All SAE will be reported in due time by the investigator to the sponsor with copy to the trial PI. Then the PI or the sponsor will request a DSMB meeting. The DSMB should give advice to the sponsor about stopping the study (temporarily or permanently) or continuing the study. The following criteria will be considered:

- The study may be stopped if a volunteer within the period 0-28 days after vaccination suffers from clinical whooping cough without laboratory demonstration of wild-type *B. pertussis*. In such a case it must be suspected that the symptoms are caused by BPZE1.
- The study may be stopped if a volunteer has a SAE which is considered by the DSMB to be most probably caused by BPZE1.

II.3. METHOD OF BLINDING AND BREAKING THE STUDY BLIND

The 16 subjects in each dosage group study will be vaccinated in a double-blind manner (active vaccine vs. placebo). That means that all trial participants and all site staff involved in participant recruitment and follow-up will be blinded to treatment assignment. Vaccine and placebo are not distinguishable at the 10^7 dose level when thawed. For higher dose levels (10^8 , 10^9), where vaccine and placebo may be distinguishable when thawed, observer-blinding will be established, by the fact that the vaccine will be prepared and administered by a study nurse not involved in any other trial procedures

Sponsor staff and laboratory staff involved in review/analysis of data are unaware of the treatment assignments. The 6 volunteers with high PRN antibodies in the control group (group 4) will be vaccinated with active vaccine (no blinding, open label).

The information if a vial contains vaccine or placebo will only be available at the statistics center (EUCLID), Lund University Hospital pharmacy (for emergency unblinding), at the manufacturer's site (Q Biologicals) and at the sponsor pharmacovigilance site.

Since access to results of the cultivation of BPZE1 from the nasopharynx samples and the antibody determination may lead to treatment unblinding, these results will be strictly controlled within the respective laboratory. The access of these results outside the laboratory will be contingent on having a previous access to the randomization list and therefore will only be authorized after the completion of

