2. Confirm that a signed ICF is on file for the subject. Perform a limited physical examination and measure vital signs (oral temperature, blood pressure, heart rate and respiratory rate) and record the information in the subject's CRF.
3. Check of temporary contraindications to vaccination.
4. Collect urine sample from females and do a dip stick pregnancy testing.
5. Collect blood samples as described in section XII.3. "Blood samples". Complete the appropriate

document provided in the investigator or delegate Site file.

6. Assign the next consecutive vial number of the given dose group to the subject (refer to section VI.4. "Screening number and randomization procedure").
7. Record the allocated vial number in the participant medical record (source document).
8. Administer the study vaccine assigned to the subject by the investigator or delegate according to the randomization described in section VI.4 "Screening number and randomization procedure" and according to section X.7 "Handling and administration of study vaccine to participants".
9. Vaccination should be administered intranasally by two tuberculin syringes, one to each nostril. The fluid and the air cushion are pushed slowly out of the tuberculin syringe to ensure administration of the total volume (400 µl) into each nostril of the volunteer. In case of volunteer sneezing or blowing nose immediately after vaccination this should be recorded in the subject's CRF, but a new vaccine dose should not be given.

The staff and the volunteer should adhere to the safety instructions described in the Standard operating procedure.

10. Observe the subject for 2 hours after vaccination for immediate adverse events and record any immediate adverse event following immunization (AEFI).
11. Give the subject the Diary and an oral thermometer.
12. Inform the subject to record in the Diary.
 - a. Any respiratory tract adverse reaction (AR) occurring until Visit 8 and to specify the intensity of the reaction using definitions given in the Diary.
 - b. Any other medical event occurring until Visit 8 and to specify the intensity of the reaction using definitions given in the Diary.
 - c. The temperature as measured orally with the provided thermometer daily in the evening from day 0 until day 28. If the temperature is taken more than once during a day the highest temperature of the day should be recorded in the Diary.
 - d. Any medication taken from day 0 until Visit 8.
13. Inform the subject to

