Vaccine and placebo are not distinguishable when frozen, allowing for allocation concealment, and are not distinguishable at the 10^7 dose level when thawed. For higher dose levels (10^8 , 10^9), where vaccine and placebo may be distinguishable when thawed, observer-blinding will be established, by the fact that the vaccine will be prepared and administered by a study nurse not involved in any other trial procedures.

The randomization list, establishing the order of vials and the correspondence between vial number and active vaccine or placebo group will be generated centrally by the statistician at the EUCLID clinical trials platform prior to the start of the study and kept confidentially in a secure environment.

The list with the codes/information if a vial contains vaccine or placebo will only be available at the statistics center (EUCLID), Lund University Hospital pharmacy (for emergency unblinding), at the manufacturer's site (Q Biological; for labelling the vials) and at the sponsor pharmacovigilance site. The decision whether the code shall be broken for an individual volunteer or all participants will be made by the investigator.

For purposes of interim analyses, the statistician responsible for the analysis will maintain the codes in strict confidence with no communication of any individual codes until final data lock.

An identical series of back up vials will be generated for each group. These vials will be kept and stored at the manufacturer's site.

VII. Prior and concomitant medications and non-study vaccines

VII.1 PRIOR MEDICATIONS AND VACCINATION

All prior medications and vaccinations will be asked for and documented (in subjects' medical record) at visit 1 and updated at visit 2 as indicated below:

The following therapies must be excluded prior to the time of the vaccination (Visit 2):

- Receipt of immunoglobulin, blood derived products, systemic corticosteroids or other immunosuppressant drugs within the previous 90 days and receipt of corticosteroids for use in the respiratory tract (e.g. nasal steroids, inhaled steroids) within 30 days prior to Visit 2.
- Non-study vaccines 30 days prior to Visit 2.

All medications received by the subject within 7 days prior to Visit 2 (Day 0) should be recorded in the CRF on page "Concomitant medications". The trade name, route, dose, start date, stop date and indication will be documented.

VII.2. CONCOMITANT MEDICATIONS AND NON-STUDY VACCINES

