It is critical that the vaccine is kept frozen at -60°C until the thawing just prior to vaccination to maintain the viability of the pertussis BPZE1 bacteria. The storage of the BPZE1 at RT should not be longer than 2 hours. It is recommended that the thawed BPZE1 solution is administered within one hour after leaving the freezer. Once the product has been thawed, it should be used. It is not allowed to freeze the product after it was thawed and to use it afterwards.

The vaccine will be kept in a locked freezer with alarm and continuous temperature monitoring (temperature charts).

- *Remember that samples which were thawed should never be refrozen.*

X.7. HANDLING AND ADMINISTRATION OF STUDY VACCINE AND PLACEBO TO PARTICIPANTS

It is critical that the vaccine is kept frozen below -60°C until the thawing just prior to vaccination to maintain the viability of the *B. pertussis* BPZE1 bacteria. Initial stability studies have shown that the BPZE1 Drug Product is very sensitive to freeze-thaw cycles and therefore the following actions must be taken to eliminate the risk of to obtain delivery of a uniform dose of BPZE1 colony forming units:

- Take the 3 cryovials out of the plastic bags immediately after removal out of the freezer
- Put the cryovials immediately in a "cryovial rack", make sure that the cryovial is in vertical position
- Check that the cryovials are not damaged.
- Leave cryovials for about 15 min at RT before administration
- **Do not invert or shake the cryovials before use**
- Attention: 1 cryovial was added as a spare vial. Do not use this spare vial without approval of the investigator or delegate.
- Extract slowly the total volume of one (1) cryovial by placing a 1 mL- tuberculine syringe on the bottom of the cryovial.
- Expel the liquid from the syringe back into the vial slowly to mix the liquid (only once!)
- ***NB! Do not remove the air present in the syringe***
- The volunteer should lay down during and 5 - 7 minutes after administration.
- Administer to one nostril the whole content of the syringe by slowly pushing the fluid and the air cushion out of the tuberculine syringe.
- Take a new 1-mL tuberculine syringe and repeat the extraction and administration procedure for the second cryovial
- Administer the whole content of the syringe to the other nostril.

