For fever, the intensity recorded in the CRF will be the highest observed temperature of the day measured oral in degrees Celsius if temperature is taken more than once a day otherwise the evening temperature.

XIII.2. RECORDING OF SAFETY PARAMETERS

Immediate AEFI

The subjects will be under the surveillance of the investigational staff for at least 2 hours following vaccination for evaluation of immediate adverse events. The subjects have to stay at the clinic in total 6 hours after vaccination.

Adverse events (respiratory tract adverse reactions and systemic adverse events, serious or not) occurring during this time period (2 hours) will have to be reported by the investigator or delegate in accordance with applicable laws (LVFS 2011:19, Patientdatalagen 2008:355).

AEFI from the respiratory tract

AEFI with difficulties in breathing (asthma, spasmodic cough, pneumonia) will be considered as serious and reported to the DSMB and sponsor. Other AEFI from the respiratory tract will be recorded in the volunteer's CRF.

After the immediate medical surveillance at the investigator site, respiratory tract adverse events occurring from the day of vaccination (Day 0) to Day 28 following vaccination will be recorded in the Diary by the subject.

- Cough will be daily documented from Day 0 to Day 28
- Spasmodic cough, defined as rapid repetitive cough without intervening inspiration usually occurring as sudden intensified attacks of involuntary coughing (paroxysms) that may occur at different times in a way that is not regular several times per 24 hours, will be daily documented from Day 0 to Day 28
- Solicited AE from the respiratory tract that are pre-listed in the Diary will be daily documented from Day 0 to Day 28.
- Unsolicited AE from the respiratory tract will be spontaneously recorded in the Diary from Day 0 to Day 28

At Visit 8, 28 days (-1: +7) after vaccination, the Diary will have to be returned to the investigational site by the subject. The investigator or delegate will check the Diary, interview the subject and record AE from the respiratory tract in the CRF.

Systemic AEFI

After the immediate medical surveillance at the investigator site, systemic adverse events occurring from the day of vaccination (Day 0) to Day 28 following vaccination will be recorded in the Diary by the subject:

- Solicited systemic adverse events (fever, headache and tiredness) that are pre-listed in the Diary will be daily documented from Day 0 to Day 28

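### At 10^8 and 10^9 cfu the plan declares participants blinded but states no measure that hides the thawed product from them, and they grade their own cough

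*Combined protocol and SAP*

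**What the plan says.** Protocol II.3 sets the intent for Groups 1 to 3: "all trial participants and all site staff involved in participant recruitment and follow-up will be blinded to treatment assignment". At 10^7 cfu the thawed products look alike. For the two higher doses, protocol II.3, VI.4 and X.4 and SAP 1.4 concede a possible visible difference ("where vaccine and placebo may be distinguishable when thawed, observer-blinding will be established") and give one means of dealing with it: "the vaccine will be prepared and administered by a study nurse not involved in any other trial procedures".

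The product is thawed by the time it reaches the volunteer. Protocol X.7 instructs: "Leave cryovials for about 15 min at RT before administration". It then has the dose drawn into a 1 mL tuberculin syringe and given with the volunteer lying down: "Administer to one nostril the whole content of the syringe by slowly pushing the fluid and the air cushion out of the tuberculine syringe". A second syringe follows for the other nostril.

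On data capture, protocol XIII.2 says "Cough will be daily documented from Day 0 to Day 28", and VI.3.3 asks the volunteer to rate intensity against definitions printed in the Diary. Under protocol XIV.1 and SAP 2.1.1, cough or spasmodic cough of grade 2 or higher is a primary endpoint event without a relatedness condition. The other two components require at least a possible relation to vaccination.

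**The concern.** The measure and the promise do not match. A dosing nurse with no other role keeps the people who assess the volunteer from seeing the product. It does nothing about the volunteer, who is present when the product is given and is the source of the cough record.

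A volunteer who guessed the product could report cough differently, and the cough component has no causality judgement to dampen this. The exposure is confined to the two higher doses. A change in reported cough between 10^7 and the higher doses could therefore partly reflect a weaker blind rather than the vaccine. The pooled placebo arm would also mix 4 recipients of a look-alike product with 8 whose product may be recognisable.

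**Working it through.** **1. Who is protected by what (10^8 and 10^9)**

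| Person | Declared blinded (II.3) | Stated measure |
|---|---|---|
| Recruitment and follow-up staff | Yes | A separate nurse prepares and gives the dose |
| Participant | Yes | None stated |
| Dosing nurse | No | Not applicable |

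X.7 is the natural place for a participant measure. It covers rack position, thaw time, a single mixing, keeping the air in the syringe, and posture. It has no screen, no opaque or wrapped syringe, and no preparation out of sight. The eye protection in II.1 and III.3 is there against droplets and is not described as masking.

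**2. The plan's own figures** (protocol XV.1, SAP 1.3)

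- Chance of at least one event in 12 at a rate of 12.6%: 1 − (1 − 0.126)^12 = 80.1%. The plan says 80%.
- Exact two-sided upper 95% bound for 0/12: 1 − 0.025^(1/12) = 26.5%. The plan prints 26%.
- The same for 0/36: 1 − 0.025^(1/36) = 9.7%. The plan prints 10%.

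These reproduce. Nothing here corrects the sample-size figures.

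**3. Exposure ceiling**

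Groups 2 and 3 each have 12 vaccine and 4 placebo recipients.

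- Randomised participants: 2 × 16 = 32 of 3 × 16 = 48 (67%).
- Vaccine recipients: 2 × 12 = 24 of 36 (67%).
- Placebo recipients: 2 × 4 = 8 of 12 (67%).

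Group 1 is not exposed, and Group 4 is open-label by design.

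**4. How far a few changed grades would move the result**

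Exact (Clopper-Pearson) 95% intervals for one vaccine arm of 12:

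| Events | 95% CI |
|---|---|
| 0/12 | 0 to 26.5% |
| 1/12 | 0.2 to 38.5% |
| 2/12 | 2.1 to 48.4% |

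Chance of at least one event, 1 − (1 − p)^12, for reported rates p that are assumptions and not in the documents:

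| p | Chance |
|---|---|
| 5% | 46% |
| 10% | 72% |
| 20% | 93% |
| 30% | 99% |

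These figures show how sensitive an arm of 12 is to one or two events of any origin. They do not measure bias.

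**5. Which escalation review is touched**

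Protocol XIII.7 has the DSMB review accumulated safety data before Group 2 and again before Group 3. The first rests on Group 1, where the products look alike. The second includes Group 2, which is exposed. SAP 3.10 puts cough of grade 2 or higher by allocation in those reports.

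**The case against.** There are several fair points on the plan's side.

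- **Declared intent.** A reader might infer that participants are unblinded by design at the higher doses. The documents do not support that: II.3 places the observer-blinding sentence under a commitment that covers participants. What is missing is a mechanism.
- **Unseen SOPs.** VI.3.3 refers to an SOP for safety instructions, and XVII.1 promises SOPs covering vaccine handling and vaccination. One of them could contain masking. This stands and limits confidence, although a protocol that claims double-blinding should state its method.
- **What the volunteer can see.** The volunteer lies down, receives 0.4 mL per nostril, and has no second product to compare. The documents say only that the products may be distinguishable. This weakens the inference without removing it. Up to five volunteers are dosed on one day at intervals of at least 1 hour (VI.2) and each stays 6 hours (VI.3.3), so their stays can overlap and impressions could be shared.
- **Staff review.** XIII.2 has the investigator or delegate check the Diary and interview the volunteer before CRF entry, and XIII.1 names a grading scale. Both still rest on the volunteer's account.
- **No comparisons.** XV.2.1 and SAP 2.2.2 plan no tests between arms or doses. Any harm is therefore to descriptive rates and to the reading of them.

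A reader might also infer from VI.3.3 ("Administer the study vaccine assigned to the subject by the investigator or delegate") that one person both doses and performs the 2-hour observation, against the nurse rule. That over-reads a generic phrase used throughout the visit lists. The delegate may differ by step, the words can equally describe who assigns the vial, and the nurse rule already keeps that nurse out of the observation.

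**Conclusion.** The point holds as a gap between a stated property and its means. At 10^8 and 10^9 cfu the plan declares participants blinded and gives no measure that would make them so, while the cough component of the primary endpoint starts from their own record and grade. The ceiling is 32 of 48 randomised participants (24 vaccine, 8 placebo). The number who would notice anything, and the direction of any bias, cannot be derived from the documents.

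Two wider conclusions are tempting and unsupported. The intervals for 0, 1 and 2 events in 12 do not estimate a bias. Nor are both escalation reviews compromised: only the one before 10^9 could be.

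The conclusion assumes that the unseen SOPs contain no masking step and that the possible difference can be seen in the syringe or during administration. Confidence is moderate. The change is worth making because it is cheap and supports the double-blind claim for two of the three randomised groups.

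**What to change.** In protocol X.7 and VI.4, require the dosing nurse in Groups 2 and 3 to:

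- thaw and draw up out of the participant's sight;
- give the dose from an opaque or sleeved syringe;
- check the fill volume before sleeving, and confirm that fluid and air cushion are fully expelled.

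The same procedure could be used in Group 1 for uniformity, but blinding there does not need it. Carry the wording into II.3, X.4 and SAP 1.4, which repeat the current text. If an existing SOP already masks the participant's view, stating that in the protocol is enough.

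If masking is not adopted, describe Groups 2 and 3 as observer-blind only, and show cough in Group 1 placebo separately from Group 2 and 3 placebo before pooling. SAP 3.4 already uses cough in placebo recipients to decide on pooling, so the addition is to report this split with the difference in blinding given as the reason. Such a split of 4 against 8 can show a large discrepancy but cannot rule one out: the exact upper 95% bound for 0/4 is 1 − 0.025^(1/4) = 60.2%.

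Cost: sleeves or tape, a short protocol and SOP change, and slightly harder visual confirmation of complete delivery. No extra staff are needed, because the separate nurse is already planned.

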Vaccine or placebo will be given as single administrations by nasal application in 0.4 mL in each nostril (0.4 mL per nostril containing half the dose 5×10^6 ; 5×10^7 ; 5×10^8 bacteria to give a total dose of 10^7 ; 10^8 ; 10^9 , respectively). The dose of BPZE1 active ingredient or placebo will be administered to the volunteer after thawing within 2 hours after leaving the freezer.

X.4. LABELLING AND PACKAGING OF STUDY VACCINE AND PLACEBO

Vials of vaccine and placebo are provided in 1.8 ml sterile polypropylene cryotubes (CE marked medical device). The vial closure system is a polypropylene screw cap (see Information Manufacturing Drug Product).

Vaccine and placebo will come in identical vials. Vaccine and placebo are not distinguishable when frozen, allowing for allocation concealment, and are not distinguishable at the 10^7 dose level when thawed. For higher dose levels (10^8 , 10^9), where vaccine and placebo may be distinguishable when thawed, observer-blinding will be established, by the fact that the vaccine will be prepared and administered by a study nurse not involved in any other trial procedures.

Per dose/group, the vials with the vaccine or placebo will be identically coded. Only the group/subject number on the vials (i.e. vial number) will be different.

Per subject, the vials (2 vials for administration and one spare vial) will be packed in a small plastic bag (outer package).

The bags with the vaccine vials or placebo vials will receive an identical label. Only the group/subject number on the bag (i.e. vial number) will be different.

The bags containing either the vaccine or the placebo will be packed in 2 boxes of 8 bags per group/dose.

Primary labels for the cryovials and secondary labels for the plastic bags are designed.

Primary labels for the 4 different groups in the BPZE1 Drug Product Phase 1 study

Group 1: Low dose

Trial code: C14-80
BPZE1 5×10^6 CFU/ Placebo-400µl
Nasal administration
Batch: XXXXXX
Retest date: DDMMYYYY
Store below -60°C
For clinical use only
Sponsor INSERM
[contact]
Patient No: 1XY*

Group 2: Middle dose

Trial code: C14-80
BPZE1 5×10^7 CFU/ Placebo -400µl
Nasal administration
Batch: XXXXXX
Retest date: DDMMYYYY
Store below -60°C
For clinical use only
Sponsor: INSERM
[contact]
Patient No: 2XY*

Group 3: High dose

Trial code: C14-80
BPZE1 5×10^8 CFU/ Placebo -400µl
Nasal administration
Batch: XXXXXX
Retest date: DDMMYYYY
Store below -60°C
For clinical use only
Sponsor: INSERM
[contact]
Patient No: 3XY*

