Group 4: High dose

Trial code: C14-80
BPZE1 5×10^8 CFU-400µl
Nasal administration
Batch: XXXXXX
Retest date: DDMMYYYY
Store below -60°C
For clinical use only
Sponsor: INSERM
[contact]
Patient No: 4XY*

*: XY varies from 01 to 16 for group 1, from 17 to 32 for group 2, from 33 to 48 for group 3 and from 49 to 54 for group 4. This corresponds to the vial number. To ensure randomized allocation, vials must be used by the site in their consecutive order of vial number within a given group.

Label for the outer package for the BPZE1 Phase 1 study

INSERM — ISP- 75013 Paris — FRANCE	[contact]
Clinical trial: C14-80 BPZE1 Phase Ib	EudraCT Number: 2015-001287-20
Nasal drops	Administration: nasal only
Produced by: Q Biologicals - Belgium	
Investigator: Karolinska University Hospital- [name]	
BPZE1 xx CFU-400 µL Batch n°: xxxxxx	
Retest date xx/xx/xxxx	Storage below - 60°C
Genetically Modified Organism	
Use under medical surveillance	
For clinical trial use only	
Group/Subject N°: XXY	

BPZE1 xx CFU is 5×10^8 CFU for group 1, 5×10^7 CFU for group 2 and 5×10^8 CFU for group 3 and 4.

Group/ Patient N° is 101 to 116 for group 1, 217 to 232 for group 2, 333 to 348 for group 3 and 449 to 454 for group 4. This corresponds to the vial number. To ensure randomized allocation; vials must be used by the site in their consecutive order of vial number within a given group.

X.5. SHIPMENT OF STUDY VACCINE AND PLACEBO

The 2 boxes containing the vaccine and placebo vials will be shipped on dry ice in boxes with temperature charts directly to the clinical trial site. The reason for not shipping the study vaccine to the local pharmacy is to minimize the risk of breaking the cold chain (see below). At the clinical center the vaccine will be stored in a freezer below -60°C.

The boxes will be shipped by a certified door-to-door service company.

- At the moment of receipt, check the temperature charts and the presence of dry ice. No temperature recording should be above -60°C
- Care must be taken to minimize the exposure to room temperature (RT) remove the material out of the dry ice box in front of the freezer with set point below -60°C

X.6. STORAGE OF STUDY VACCINE AND PLACEBO

Frozen storage, below -60°C at the clinical trial site.

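### Protocol X.4 specifies an outer-bag strength for Group 1 that is 100 times the strength on the vials inside the bag, and equal to that of Groups 3 and 4

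*Combined protocol and SAP*

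**What the plan says.** Section X.4 of the protocol specifies two layers of labelling: a primary label on each cryovial and a secondary label on the plastic bag that holds one subject's vials. Each bag contains "2 vials for administration and one spare vial".

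The bag label template has a strength field, "BPZE1 xx CFU-400 µL". A sentence below the template fills it in by group: "BPZE1 xx CFU is 5×10^8 CFU for group 1", then "5×10^7 CFU for group 2 and 5×10^8 CFU for group 3 and 4".

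The primary labels in the same section use the same 400 µl basis. Group 1 reads "BPZE1 5×10^6 CFU/ Placebo-400µl" and Group 3 reads "BPZE1 5×10^8 CFU/ Placebo -400µl". The Group 2 and Group 4 vial labels carry 5×10^7 and 5×10^8.

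Section X.3 describes an ascending sequence of doses and states that each nostril receives "half the dose 5×10^6 ; 5×10^7 ; 5×10^8 bacteria to give a total dose of 10^7 ; 10^8 ; 10^9", in that order. The synopsis repeats these per-nostril and total figures. The synopsis, protocol VI.2 and SAP 1.2.1 all give Group 1 a dose of 10^7 cfu.

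**The concern.** Within one section, the bag and the vials it contains are given different strengths for Group 1 on the same volume basis. The bag figures for Groups 1, 2 and 3 run 5×10^8, 5×10^7, 5×10^8. That is not an ascending sequence, and it gives the lowest dose group the bag strength of the highest.

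The bag is the unit that is stored and retrieved. Under X.5 the product goes straight to the clinical site without passing through the local pharmacy. The receipt checks listed there concern temperature charts and dry ice. The handling steps in X.7 include no comparison of bag strength with vial strength. The protocol therefore describes no step at the site that would be sure to bring the conflict to light before use.

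The figure is not a trivial one. According to III.2, the first study in man went no higher than 10^7 cfu, and VI.2 and XIII.7 place a safety board review of 28-day data before each escalation. A Group 1 bag would carry a strength that belongs to the level beyond those reviews. Staff who noticed the mismatch on a dosing day would have to decide, with the product thawing, whether it may be used.

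**Working it through.** **Inputs.** Bag strengths come from the X.4 outer-package sentence, vial strengths from the X.4 primary labels, planned totals from X.3 and VI.2, and two vials administered per subject from X.4.

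**Formulas.** Total per subject = 2 × labelled strength. Conflict = bag strength ÷ vial strength.

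| Group | Planned total | Vial label, per 400 µl | 2 × vial | Bag label, per 400 µl | 2 × bag | Bag ÷ vial |
|---|---|---|---|---|---|---|
| 1 | 10^7 | 5×10^6 | 10^7 | 5×10^8 | 10^9 | 100 |
| 2 | 10^8 | 5×10^7 | 10^8 | 5×10^7 | 10^8 | 1 |
| 3 | 10^9 | 5×10^8 | 10^9 | 5×10^8 | 10^9 | 1 |
| 4 | 10^9 | 5×10^8 | 10^9 | 5×10^8 | 10^9 | 1 |

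The vial labels reproduce the planned total in all four groups. The bag labels do so in Groups 2, 3 and 4 and fail in Group 1, where 5×10^8 ÷ 5×10^6 = 100.

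**Could the bag figure be on a different basis?** The template states 400 µl, as the vial labels do, but two other readings are worth trying.

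- *Total administered per bag (two vials).* Group 1 would need 10^7, and 5×10^8 ÷ 10^7 = 50, so it still fails. Groups 2 to 4 would then fail as well: 5×10^7 against 10^8, and 5×10^8 against 10^9.
- *Total content of the bag, spare included (three vials).* Group 1 would need 3 × 5×10^6 = 1.5×10^7, and 5×10^8 ÷ 1.5×10^7 is about 33. Group 2 would need 1.5×10^8 and Groups 3 and 4 would need 1.5×10^9, so no group matches.

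Only the per-vial reading fits Groups 2, 3 and 4. Under that reading, Group 1 alone is out of line.

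**The case against.** The strongest objection is that everything turns on one superscript digit. When a PDF is converted to text, a raised 6 can come out as an 8, and that would not be an error in the plan. The converted text may contain such a slip elsewhere: in the I.4 flow chart, the Visit 3 blood volume carries a footnote mark with no matching note. Against this, 5×10^6 reads correctly in the synopsis, in X.3 and on the Group 1 vial label, so the figure is not misread systematically. The text alone cannot separate a conversion slip from a typing error in the protocol, so the page must be checked first. This part of the objection stands.

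The second objection concerns consequences, and it too largely stands. A reader might infer three things that the documents do not support.

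- *That only the subject number separates the lowest from the highest dose.* The vials carry their own strength. Bags are boxed by group and dose. The first digit of the subject number encodes the group (101 to 116 against 333 to 348). Groups are dosed consecutively, with at least 6 weeks' follow-up of each before the next is vaccinated.
- *That Group 1 volunteers would receive 100 times the planned dose.* VI.4 and X.4 have the site select product by consecutive vial number within the dose group, not by the strength on the bag. The conflict is between label texts. The documents show no route from it to a dosing error, and 4 of the 16 Group 1 bags hold placebo in any case.
- *That accountability records would fail to match the vials.* X.8 lists quantities delivered, in stock, administered, wasted or lost, and destroyed. It does not say that bag strength is recorded or reconciled.

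The documents also give a label design and template. They do not show what was printed.

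**Conclusion.** As the text stands, the X.4 outer-package specification for Group 1 conflicts with the Group 1 vial label and the dosing text by a factor of exactly 100, and it equals the entry for Groups 3 and 4. No alternative basis for the bag figure removes the conflict. The conclusion assumes that the superscript is an 8 on the protocol page.

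The point is confined to one entry in one sentence. The vial labels and dosing passages agree with each other in every group, and no endpoint, sample-size or analysis figure depends on the bag label. It should still be settled before labels are released. This is operative labelling text for a live genetically modified organism in a dose-escalation study, and a bag that contradicts its contents is a safety error in the labelling even with other safeguards in place. Which passage is wrong is for the sponsor to establish from the product dossier.

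**What to change.** 1. Check the protocol page to rule out a misread superscript. If the page shows the same figure as the vial label, the point falls away.
2. If the conflict is on the page, reconcile the X.4 outer-package sentence with the Group 1 primary label, X.3 and the product dossier, and correct whichever passage is wrong.
3. Proof the bag labels for all four groups against the vial labels before release, and reprint any that have already been produced with the conflicting figure.

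The cost is one corrected line and a proof check, plus a reprint of the 16 Group 1 bag labels if they already exist. No change to the accountability form is needed, and no part of the statistical analysis changes.
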